APPENDIX 4 WOMEN OF CHILDBEARING POTENTIAL DEFINITIONS AND METHODS OF CONTRACEPTION

DEFINITIONS

WOMAN OF CHILDBEARING POTENTIAL (WOCBP)

A woman is considered fertile following menarche and until becoming post-menopausal unless permanently sterile. Permanent sterilization methods include hysterectomy, bilateral salpingectomy, and bilateral oophorectomy.

WOMEN IN THE FOLLOWING CATEGORIES ARE NOT CONSIDERED WOCBP

- Premenarchal
- Premenopausal female with 1 of the following:
 - Documented hysterectomy
 - Documented bilateral salpingectomy
 - Documented bilateral oophorectomy

Note: Documentation can come from the site personnel's review of the participant's medical records, medical examination, or medical history interview.

- Postmenopausal female
 - A postmenopausal state is defined as 12 months of amenorrhea in a woman over age 45 years in the absence of other biological or physiological causes. In addition, females under the age of 55 years must have a serum follicle stimulating hormone, (FSH) level > 40 mIU/mL to confirm menopause.

Note: Females treated with hormone replacement therapy, (HRT) are likely to have artificially suppressed FSH levels and may require a washout period in order to obtain a physiologic FSH level. The duration of the washout period is a function of the type of HRT used. The duration of the washout period below are suggested guidelines and the investigators should use their judgement in checking serum FSH levels.

- 1 week minimum for vaginal hormonal products (rings, creams, gels)
- 4 week minimum for transdermal products
- 8 week minimum for oral products

Other parenteral products may require washout periods as long as 6 months. If the serum FSH level is > 40 mIU/ml at any time during the washout period, the woman can be considered postmenopausal.

CONTRACEPTION GUIDANCE FOR FEMALE PARTICIPANTS OF CHILD BEARING POTENTIAL

One of the highly effective methods of contraception listed below is required during study duration and until the end of relevant systemic exposure, defined as 5 months after the end of study treatment.

Local laws and regulations may require use of alternative and/or additional contraception methods.

Highly Effective Contraceptive Methods That Are User Dependent

Failure rate of <1% per year when used consistently and correctly.^a

- Combined (estrogen- and progestogen-containing) hormonal contraception associated with inhibition of ovulation^b
 - oral
 - intravaginal*
 - transdermal*
- Progestogen-only hormonal contraception associated with inhibition of ovulation^b
 - oral
 - injectable*

Highly Effective Methods That Are User Independent

- Implantable progestogen-only hormonal contraception associated with inhibition of ovulation^b
- Intrauterine device (IUD)^c
- Intrauterine hormone-releasing system (IUS)^c
- Bilateral tubal occlusion
- Vasectomized partner

A vasectomized partner is a highly effective contraception method provided that the partner is the sole male sexual partner of the WOCBP and the absence of sperm has been confirmed. If not, an additional highly effective method of contraception should be used.

NOTES:

^a Typical use failure rates may differ from those when used consistently and correctly. Use should be consistent with local regulations regarding the use of contraceptive methods for participants participating in clinical studies.

^b Hormonal contraception may be susceptible to interaction with the study drug, which may reduce the efficacy of the contraceptive method. Hormonal contraception is permissible only when there is sufficient evidence that the IMP and other study medications will not alter hormonal exposures such that contraception would be ineffective or result in increased exposures that could be potentially hazardous. In this case, alternative methods of contraception should be utilized.

^c Intrauterine devices and intrauterine hormone releasing systems are acceptable methods of contraception in the absence of definitive drug interaction studies when hormone exposures from intrauterine devices do not alter contraception effectiveness

* Not approved in Japan

CONTRACEPTION GUIDANCE FOR MALE PARTICIPANTS WITH PARTNER(S) OF CHILD BEARING POTENTIAL.

Male participants with female partners of childbearing potential are eligible to participate if they agree to the following during the treatment and until the end of relevant systemic exposure.

- Inform any and all partner(s) of their participation in a clinical drug study and the need to comply with contraception instructions as directed by the investigator.
- Male participants are required to use a condom for study duration and until the end of relevant systemic exposure defined as 7 months after the end of treatment in the male participant.
- Female partners of males participating in the study to consider use of effective methods of contraception until the end of relevant systemic exposure, defined as 5 months after the end of treatment in the male participant.
- Male participants with a pregnant or breastfeeding partner must agree to remain abstinent from penile vaginal intercourse or use a male condom during each episode of penile penetration during the treatment and until 7 months after the end of treatment.
- Refrain from donating sperm for the duration of the study treatment and for 7 months after the end of treatment.

COLLECTION OF PREGNANCY INFORMATION

Guidance for collection of Pregnancy Information and outcome of pregnancy on the Pregnancy Surveillance Form is provided in [Section 9.2.5](#) and the Appendix for Adverse Events and Serious Adverse Events Definitions and procedures for Evaluating, Follow-up and Reporting

APPENDIX 5 SIMULATION TO EXAMINE MTPI VS. TRADITIONAL 3+3 FOR DOSE ESCALATION STUDY WITH 2 DOSE LEVELS

The dose escalation part of the study utilizes the mTPI method. The mTPI uses a set of decision rules guided by simple Bayesian models and requires a definition of an equivalence interval (EI), in which any dose is considered close to the true maximum tolerated dose (MTD). For this study, the EI is defined as [20%, 30%] with the target toxicity rate of 25%. With this method, there are 3 intervals in the toxicity probability scale: (0, 20%) that is considered lower than the target toxicity rate, [20, 30%] that is considered within the toxicity target range, and (30, 100%) that is considered toxic.

Using this mTPI design, initially 3 eligible subjects will be treated at the dose level of 2 mg/kg. An additional 3 subjects may be added to the same dose level, and hence a total number of 3 to 6 subjects will be treated for a given dose level. A decision to consider the next higher dose level (4 mg/kg) or stop the enrollment will be guided by the number of subjects with dose-limiting toxicities (DLTs) observed (see Table 1). Basically 3 or 6 subjects will be enrolled in a cohort. However, if additional subject will be enrolled in a cohort (e.g. 4 or 7 subjects), dose escalation will be guided by Table 1.

Table 1: Guidance for Dose Escalation/De-escalation Based on Observed Toxicity Outcomes

		Number of Subjects Treated					
		3	4	5	6	7	8
Number of Subjects with DLTs	0	E	E	E	E	E	E
	1	S	E	E	E	E	E
	2	D	D	S	S	S	S
	3	DU	DU	DU	D	S	S
	4				DU	DU	D
	5						DU
	6						

At Starting dose (2 mg/kg):

E: The current dose level is safe. Escalate and enroll subjects to the next higher dose level (4 mg/kg). If the next higher dose level (4 mg/kg) is deemed to be unacceptably toxic (DU) or has already enrolled 6 or more subjects with D, accept the current dose (2 mg/kg).

S: If 6 or more subjects have already enrolled at this dose level, accept the current dose level (2 mg/kg). Otherwise, stay current dose and enroll 3 additional subjects.

D/DU: The current dose (2 mg/kg) is toxic, stop the enrollment.

At Maximum dose (4 mg/kg):

E: The current dose level is safe. Accept the current dose (4 mg/kg).

S: If 6 or more subjects have already enrolled at this dose level, accept the current dose level (4 mg/kg). Otherwise, stay current dose and enroll 3 additional subjects.

D: De-escalate to the lower dose level (2 mg/kg). Accept the lower dose level (2 mg/kg) if 6 or more subjects have already been enrolled at the lower dose level (2 mg/kg).

DU: The current dose is unacceptably toxic. De-escalate to the lower dose level (2 mg/kg) without re-escalation to the current dose level (4 mg/kg). Accept the lower dose level (2 mg/kg) if 6 or more subjects have already been enrolled at the lower dose level (2 mg/kg).

DU: The current dose is unacceptably toxic. De-escalate to the lower dose level (2 mg/kg) without re-escalation to the current dose level (4 mg/kg). Accept the lower dose level (2 mg/kg) if the maximum of 6 subjects have already been enrolled at the lower dose level (2 mg/kg).

Simulations were conducted to examine the performances of the mTPI design and the traditional escalation A+B designs (including a 3+3 design) for this study. The 3+3 design starts from the lower dose level (2 mg/kg); adapts every cohort of 3 patients; considers the next dose level if unacceptable toxicity rate observed. The “1/3” rule has been used in the designs, in the way that:

- If the observed toxicity rate is < 1/3 in the initial cohort of subjects (3 subjects for the 3+3 design), then this dose level will be considered safe, and proceeding with the next higher dose level will be discussed
- If the observed toxicity rate is < 1/3 in the last cohort of subjects (3 subjects for the 3+3 design), then another 3 subjects will be enrolled to evaluate the safety at a max cohort.
- If the observed toxicity rate is 1/3 in the first cohort of subjects, then another 3 subjects will be enrolled to evaluate this dose level further;
- If the observed toxicity rate is > 1/3 in the first cohort of subjects, then this dose level will be considered too toxic and stop enrollment;
- If the observed toxicity rate is < 1/3 at a max cohort size (6 subjects in total for the 3+3 design), then this dose level will be considered safe and proceeding with the next higher dose level will be discussed;
- If the observed toxicity rate is ≥ 1/3 at a max cohort size (6 subjects in total for the 3+3 design), then this dose level will be considered as too toxic.

The mTPI design is knowledge-driven, which assumes a target toxicity rate. On the contrary, the traditional 3+3 design is algorithm-driven, which uses the “1/3” rule.

Simulation Implementation:

- 10,000 simulated trials
- Target toxicity rate for the mTPI design: 25% with EI = [20, 30%]
- mTPI design as described above
- Traditional 3+3 design as described above

Table 2 **Dose-Toxicity Scenarios**

Scenario	True DLT Rate	
	2 mg/kg	4 mg/kg
1	0.1	0.15

Table 2 Dose-Toxicity Scenarios

Scenario	True DLT Rate	
	2 mg/kg	4 mg/kg
2	0.1	0.2
3	0.15	0.25
4	0.20	0.25
5	0.25	0.33

Simulation Results:

Simulation results are summarized from all the simulated trials per scenario, and include the following statistics:

- Selected (%): Frequency of each dose level being selected as acceptable dose level.
- DLT rate: The average number of subjects who have DLT across all dose levels.
- Average Sample Size: The average number of subjects across all dose levels.

Table 3 Simulation Results

Scenario	Designs	Items	Selected (%)		DLT Rate	Average Sample Size
			Under 2 mg/kg	2 mg/kg		
1	True DLT rate			0.1	0.15	
	mTPI	Selected (%)	3.49	10.74	85.77	12.4
	3+3	Selected (%)	9.93	19.84	70.23	12.8
2	True DLT rate			0.1	0.2	
	mTPI	Selected (%)	3.55	15.29	81.16	14.9
	3+3	Selected (%)	10.16	30.36	59.48	15.3
3	True DLT rate			0.15	0.25	
	mTPI	Selected (%)	8.19	25.13	66.69	19.6
	3+3	Selected (%)	20.49	36.15	43.36	19.8
4	True DLT rate			0.2	0.25	
	mTPI	Selected (%)	14.65	27.50	57.85	22.1
	3+3	Selected (%)	31.84	30.66	37.50	22.3
5	True DLT rate			0.25	0.33	
	mTPI	Selected (%)	22.46	37.17	40.36	28.0
	3+3	Selected (%)	44.17	34.17	21.67	28.0

In summary, the mTPI design selects the correct dose level more frequently than the traditional 3+3 designs for under the true toxicity rate within EI evaluated. The average toxicity rates for mTPI design are slightly lower than the rates of the traditional designs. The traditional 3+3 designs are more conservative and may select sub-optimal dose frequently.

APPENDIX 6 AE MANAGEMENT FOR CABIRALIZUMAB MONOTHERAPY COHORTS

Hepatic Adverse Event Management without Liver Metastasis		
Grade of Liver Test Elevation	Management	Follow-Up
AST or ALT $>3.0 \times \text{ULN}$ and Total bilirubin $>2 \times \text{ULN}$ or INR > 1.5	
 – Discontinue cabiralizumab therapy per protocol 	
 – Continue LFT monitoring per protocol until resolution. – Continue monitoring for and other associated clinical signs or symptoms – Contact the Medical Monitor – Evaluate for non-drug related causes of the laboratory abnormalities (e.g. obstruction, viral infection, Gilbert's disease, etc) – Under selected circumstances (e.g alternative etiology is identified), patient may receive additional therapy only after consultation and agreement between the Sponsor/MM and the investigator if receiving additional treatment with cabiralizumab is in the best interest of the patient (e.g if the subject has demonstrated a response to therapy)
AST or ALT > 5 to $\leq 12 \times \text{ULN}$ and Total bilirubin $\leq 2 \times \text{ULN}$	
 – Continue cabiralizumab therapy if there are no clinical signs of significant muscle or hepatic damage – Increase frequency of monitoring of AST, ALT, bilirubin, alkaline phosphatase and INR (every 48-72 hours or more frequently, as clinically indicated) – Monitor for other clinical symptoms (fatigue, nausea, vomiting, abdominal pain, fever, rash, and/or eosinophilia) 	
 – Contact the Medical Monitor if there are clinical signs of muscle or hepatic injury or other clinical symptoms – Contact the Medical Monitor if there is a concurrent increase of bilirubin, AST, ALT, or alkaline phosphatase from baseline. – Notify the Medical Monitor if there is an AST increase $> 5 \times \text{ULN}$ – Frequency of retesting can decrease to once a week or less if abnormalities stabilize or the trial drug has been discontinued and the subject is asymptomatic – Consider gastroenterology or hepatology referral
AST or ALT >12 to $\leq 20 \times \text{ULN}$ and Total bilirubin $\leq 2 \times \text{ULN}$ or Isolated total bilirubin > 2 to $\leq 3 \times \text{ULN}$	
 – Delay cabiralizumab therapy per protocol – Increase frequency of monitoring (including but not limited to) of AST, ALT, bilirubin, alkaline phosphatase and INR (every 48-72 hours or more frequently, as clinically indicated) – Monitor for other clinical symptoms (fatigue, nausea, vomiting, abdominal pain, fever, rash, and/or eosinophilia) – Consider imaging to rule out obstruction 	
If AST and ALT $\leq 12 \times \text{ULN}$ for ≤ 28 days:
 
 – Resume routine monitoring – Resume cabiralizumab therapy at same dose level per protocol 
If elevations persist at same level for > 28 days or worsen:
 
 – Discontinue cabiralizumab therapy per protocol – Discuss with Medical Monitor
AST or ALT $> 20 \times \text{ULN}$ or Total bilirubin $>3 \times \text{ULN}$	
 – Discontinue cabiralizumab therapy 	
 – Continue LFT monitoring per protocol until resolution – Continue monitoring for and other associated clinical signs or symptoms

Hepatic Adverse Event Management with Liver Metastasis		
Grade of Liver Test Elevation	Management	Follow-Up
AST or ALT $>3.0 \times \text{ULN}$ and Total bilirubin $>2 \times \text{ULN}$ or INR > 1.5	
 – Discontinue cabiralizumab therapy per protocol 	
 – Continue LFT monitoring per protocol until resolution. – Continue monitoring for and other associated clinical signs or symptoms – Contact the Medical Monitor – Evaluate for non drug related causes of the laboratory abnormalities (e.g. obstruction, viral infection, Gilbert's disease, etc) – Under selected circumstances (e.g alternative etiology is identified), patient may receive additional therapy only after consultation and agreement between the Sponsor/MM and the investigator if receiving additional treatment with cabiralizumab is in the best interest of the patient (e.g if the subject has demonstrated a response to therapy)
AST or ALT > 5 to $\leq 12 \times \text{ULN}$ and Total bilirubin $\leq 2 \times \text{ULN}$	
 – Continue cabiralizumab therapy if there are no clinical signs of significant muscle or hepatic damage – Increase frequency of monitoring of AST, ALT, bilirubin, alkaline phosphatase and INR (every 48-72 hours or more frequently, as clinically indicated) – Monitor for other clinical symptoms (fatigue, nausea, vomiting, abdominal pain, fever, 	
 – Contact the Medical Monitor if there are clinical signs of muscle or hepatic injury or other clinical symptoms – Contact the Medical Monitor if there is a concurrent increase of bilirubin, AST, ALT, or alkaline phosphatase from baseline. – Notify the Medical Monitor if there is an AST increase $> 5 \times \text{ULN}$ – Frequency of retesting can decrease to once a week or less if abnormalities stabilize or the trial drug has been discontinued and the subject is asymptomatic – Consider gastroenterology or hepatology referral
AST or ALT >12 to $\leq 20 \times \text{ULN}$ and Total bilirubin $\leq 2 \times \text{ULN}$ or Isolated total bilirubin >3.0 to $\leq 5 \times \text{ULN}$	
 – Delay cabiralizumab therapy per protocol – Increase frequency of monitoring (including but not limited to) of AST, ALT, bilirubin, alkaline phosphatase and INR (every 48-72 hours or as clinically indicated) – Monitor for other clinical symptoms (fatigue, nausea, vomiting, abdominal pain, fever, rash, and/or eosinophilia) – Consider imaging to rule out obstruction 	
If AST and ALT $\leq 12 \times \text{ULN}$ for ≤ 28 days:
 
 – Resume routine monitoring – Resume cabiralizumab therapy at same dose level per protocol 
If elevations persist at same level for > 28 days or worsen:
 
 – Discontinue cabiralizumab therapy per protocol Discuss with Medical Monitor
AST or ALT $> 20 \times \text{ULN}$ or Total bilirubin $> 5 \times \text{ULN}$	
 – Discontinue cabiralizumab therapy 	
 – Continue LFT monitoring per protocol until resolution – Continue monitoring for and other associated clinical signs or symptoms

Periorbital Edema Adverse Event Management		
Grade of Periorbital Edema (NCI CTCAE v 4.03)	Management	Follow-Up
Grade 1	– Continue dosing cabiralizumab therapy per protocol	If worsens: – Follow as stated below
Grade 2	– Delay cabiralizumab therapy per protocol	If returns to Grade 1 or baseline before the next dosing visit: – Resume cabiralizumab therapy at same dose level without delay – Routine eye monitoring per protocol, if clinically stable If swelling persists >14 days but returns back to baseline or Grade 1 within 28 days: – Continue cabiralizumab therapy upon resolution – If it recurs at Grade 2 or above, discontinue cabiralizumab therapy
Grade ≥3	– Discontinue cabiralizumab therapy per protocol.	If returns to Grade 1 after discontinuation: – Follow up until resolution

Infusion Reactions Adverse Event Management		
Grade of Infusion Reactions (NCI CTCAE v 4.03)	Management	Follow-Up
Grade 1	
 - Decrease infusion rate of cabiralizumab therapy per protocol and restart at normal infusion rate once symptoms subside. - Monitor patient and start symptomatic treatment as clinically indicated which includes antihistamines and NSAIDs 	
If infusion reaction symptoms subside within 3 hours of cabiralizumab therapy:
 
 - Subsequent dosing should include prophylactic pre-infusion medications for cabiralizumab therapy - Continue cabiralizumab dosing at same level
Grade 2	
 - Interrupt cabiralizumab infusion - Systemic treatment including NSAIDs, corticosteroids, and antihistamines - Normal saline infusion and constant monitoring of vitals and other parameters - If symptoms resolve, resume infusion at 50% of the infusion rate and then increase to 100% if clinically stable 	
 - Resume cabiralizumab therapy at same dose level - Future dosing with pre-infusion prophylactic medications recommended including antihistamines, NSAIDs, and corticosteroids up to 25 mg as needed 
If symptoms recur:
 
 - Discontinue treatment at the visit
Grade ≥ 3	
 - Discontinue cabiralizumab therapy per protocol - Follow institutional guidelines for hypersensitivity reaction - Systemic treatment including NSAIDs, corticosteroids and antihistamines - Normal saline infusion and constant monitoring of vitals and other parameters - Bronchodilators as clinically indicated with or without hospitalization 	
If returns to Grade 1 after discontinuation:
 
 - Systemic treatment including tapering steroids, NSAIDs, and antihistamines until resolution as needed - Follow up until resolution

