^a If the AE requiring dose delay was due to one of the study drugs, the non-offending drug may be continued, taking into account the safety and clinical benefit to the patient.

^b If the AE requiring discontinuation was due to one of the study drugs, the non-offending drug may be continued, if there is timely resolution of AE and clinical benefit is shown by patient.

^c Patients on IV steroids may be switched to an equivalent dose of oral corticosteroids (e.g. prednisone) at start of tapering or earlier, once sustained clinical improvement is observed. Lower bioavailability of oral corticosteroids should be taken into account when switching to the equivalent dose of oral corticosteroids.

Hepatic Adverse Event Management without Liver Metastasis

Rule out noninflammatory causes. If a noninflammatory cause is identified, treat accordingly and continue nivolumab therapy. Consider imaging for obstruction.

Grade of Liver Test Elevation	Management	Follow-Up
AST or ALT >3.0x ULN and Total bilirubin >2x ULN or INR > 1.5	
 – Discontinue cabiralizumab and nivolumab per protocol – Start steroids 	
 – Continue LFT monitoring per protocol until resolution. – Continue monitoring for and other associated clinical signs or symptoms – Contact the Medical Monitor – Evaluate for non drug related causes of the laboratory abnormalities (e.g. obstruction, viral infection, Gilbert's disease, etc) – Under selected circumstances (e.g alternative etiology is identified), patient may receive additional therapy only after consultation and agreement between the Sponsor/MM and the investigator if receiving additional treatment with cabiralizumab and nivolumab is in the best interest of the patient (e.g if the subject has demonstrated a response to therapy)

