AST or ALT > 12 to ≤ 20 xULN and Total bilirubin ≤ 2 xULN or Isolated total bilirubin > 2 to ≤ 3 xULN	
 – Delay cabiralizumab and nivolumab therapy per protocol^a – Increase frequency of monitoring of (including but not limited to) AST, ALT, bilirubin, alkaline phosphatase and INR (every 48-72 hours or more frequently, as clinically indicated) – If there is a 2-fold ALT increase compared to the previous measurement, start steroids immediately – Consider steroid treatment on any total bilirubin increase of over 2.0x ULN – If there is a concurrent increase of alkaline phosphatase along with ALT, start steroids immediately 	
If AST/ALT return to ≤ 12 xULN within ≤ 7 days:
 
 – Resume routine monitoring – Resume cabiralizumab and nivolumab therapy at same dose level per protocol 
If elevations persist and remain at the same level > 7 days but ≤ 28 days:
 
 – Start steroids immediately and discontinue further dosing – Continue monitoring and consider dosing the subject with nivolumab therapy at the same dose level. – Consider tapering steroids over at least 1 month 
If elevations persist at the same level > 28 days or worsen:
 
 – Discontinue cabiralizumab and nivolumab therapy per protocol – 0.5-1 mg/kg/day methylprednisolone or oral equivalent and when LFT returns to Grade 1 or baseline, taper steroids over at least 1 month – Consider prophylactic antibiotics for opportunistic infections – Discuss with Medical Monitor

Hepatic Adverse Event Management without Liver Metastasis

Rule out noninflammatory causes. If a noninflammatory cause is identified, treat accordingly and continue nivolumab therapy. Consider imaging for obstruction.

Grade of Liver Test Elevation	Management	Follow-Up
	
 Monitor for other clinical symptoms (fatigue, nausea, vomiting, abdominal pain, fever, rash, and/or eosinophilia) 	

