AST or ALT >3.0x ULN and Total bilirubin >2x ULN or INR > 1.5	
 – Discontinue cabiralizumab and nivolumab therapy per protocol – Start steroids 	
 – Continue LFT monitoring per protocol until resolution. – Continue monitoring for and other associated clinical signs or symptoms – Contact the Medical Monitor – Evaluate for non drug related causes of the laboratory abnormalities (e.g. obstruction, viral infection, Gilbert's disease, etc) – Under selected circumstances (e.g alternative etiology is identified), patient may receive additional therapy only after consultation and agreement between the Sponsor/MM and the investigator if receiving additional treatment with cabiralizumab and nivolumab is in the best interest of the patient (e.g if the subject has demonstrated a response to therapy)
AST or ALT > 5 to \leq 12 xULN and Total bilirubin \leq 2 xULN	
 – Continue cabiralizumab and nivolumab therapy if there are no clinical signs of significant muscle or hepatic damage – Increase frequency of monitoring of AST, ALT, bilirubin, alkaline phosphatase and INR (every 48-72 hours or more frequently, as clinically indicated) – Monitor for other clinical symptoms (fatigue, nausea, vomiting, abdominal pain, fever, rash, and/or eosinophilia) 	
 – Contact the Medical Monitor if there are clinical signs of muscle or hepatic injury or other clinical symptoms – Contact the Medical Monitor if there is a concurrent increase of bilirubin, AST, ALT, or alkaline phosphatase – Notify the Medical Monitor if there is an AST or ALT increase > 5 xULN – Frequency of retesting can decrease to once a week or less if abnormalities stabilize or the trial drug has been discontinued and the subject is asymptomatic. – Consider gastroenterology or hepatology referral

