AST or ALT > 12 to \leq 20 xULN and Total bilirubin \leq 2 xULN or Isolated total bilirubin > 3.0 to \leq 5 xULN	
 – Delay cabiralizumab and nivolumab therapy per protocol^a – Increase frequency of monitoring of (including but not limited to) AST, ALT, bilirubin, alkaline phosphatase and INR (every 48-72 hours or more frequently, as clinically indicated) – If there is a 2-fold ALT increase compared to the previous measurement, start steroids immediately – Consider steroid treatment on any total bilirubin increase of over 2.0x ULN 	
If AST/ALT return to \leq 12 xULN within \leq 7 days:
 
 – Resume routine monitoring, resume cabiralizumab and nivolumab therapy at same dose level per protocol 
If elevations persist and remain at the same level > 7 days but \leq 28 days:
 
 – Start steroids immediately and discontinue further dosing – Continue monitoring and consider dosing the subject with nivolumab therapy at the same dose level – Consider tapering steroids over at least 1 month 
If elevations persist at the same level > 28 days or worsen:

Hepatic Adverse Event Management with Liver Metastasis

Rule out noninflammatory causes. If a noninflammatory cause is identified, treat accordingly and continue nivolumab therapy. Consider imaging for obstruction.

Grade of Liver Test Elevation	Management	Follow-Up
	
 If there is a concurrent increase of alkaline phosphatase along with ALT, start steroids immediately Monitor for other clinical symptoms (fatigue, nausea, vomiting, abdominal pain, fever, rash, and/or eosinophilia) 	
 Discontinue cabiralizumab and nivolumab therapy per protocol 0.5–1 mg/kg/day methylprednisolone or oral equivalent and when LFT returns to Grade 1 or baseline, taper steroids over at least 1 month Consider prophylactic antibiotics for opportunistic infections Discuss with Medical Monitor

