APPENDIX 8 LABORATORY ABNORMALITIES MANAGEMENT TABLE

Laboratory Abnormalities Management (CK and LDH)		
Grade of Liver Test Elevation	Management	Follow-Up
CK > 10 xULN	
 – Consider measuring CK isoenzymes as clinically indicated 	
If CK isoenzymes are abnormal
 
 – Consider checking troponin levels – Consider other assessments (including uromyoglobin) as clinically indicated 
If CK isoenzymes are normal
 
 – Continue dosing, per protocol – Monitor CK level as clinically indicated
CK or LDH > 15 to \leq 20 xULN	
 – Delay cabiralizumab and nivolumab therapy per protocol^a – Measure CK isoenzyme panel to identify source of elevation – Increase frequency of monitoring (every 48-72 hours, or more, as clinically indicated) – Notify the Medical Monitor 	
If returns to \leq 15 xULN within \leq 28 days:
 
 – Resume routine monitoring, resume cabiralizumab and nivolumab therapy at same dose level per protocol – If CK isoenzyme panel is normal continue monitoring the subject. – If CK isoenzyme panel is abnormal then consider measuring troponins. – If troponins are abnormal, contact Medical Monitor to determine if the subject can be retreated. 
If elevations persist at the same level > 28 days or worsen:
 
 – Discontinue further dosing – Discuss with Medical Monitor
CK or LDH > 20 xULN	
 – Discontinue cabiralizumab and nivolumab therapy 	
 – Follow up until resolution

a. If the AE requiring dose delay was due to one of the study drugs, the non-offending drug may be continued, taking into account the safety and clinical benefit to the patient.

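### The hepatic hold rows in Protocol Appendices 6 and 7 delay dosing for isolated bilirubin, but their restart condition names only AST/ALT

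*Protocol*

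**What the plan says.** Appendix 6 (monotherapy) and Appendix 7 (combination) each hold two hepatic tables, one for subjects without liver metastasis and one for subjects with it. Three parts of each table matter here.

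- **First row, discontinue.** In Appendix 7 the criterion is "AST or ALT >3.0x ULN and Total bilirubin >2x ULN or INR > 1.5". The Appendix 6 tables use the same limits, including "Total bilirubin $>2 \times \text{ULN}$ or INR > 1.5". The tables for subjects with liver metastasis keep the same bilirubin limit ("Total bilirubin >2x ULN or INR > 1.5").
- **Third row, delay.** There are two alternative triggers. The first is AST/ALT >12 to ≤20 x ULN with bilirubin ≤2 x ULN. The second, without liver metastasis, is "Isolated total bilirubin > 2 to ≤ 3 xULN"; with liver metastasis the band is >3 to ≤5 x ULN.
- **Follow-up for that row.** Both Appendix 6 tables allow dosing to resume under "If AST and ALT $\leq 12 \times \text{ULN}$ for ≤ 28 days". The two Appendix 7 tables use "If AST/ALT return to ≤ 12 xULN within ≤ 7 days" and "If AST/ALT return to \leq 12 xULN within \leq 7 days". The remaining branches deal with elevations that stay at the same level or worsen.

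Protocol Section 7.4.1 has dosing resume once the re-treatment criteria are satisfied. Section 7.4.2 allows it when the drug-related event has resolved in the way the appendix tables describe. Section 8.1.1 sets the permanent stop at bilirubin >3 x ULN (>5 with liver metastases).

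**The concern.** The row holds a subject for one analyte and releases the subject on another. A site with a subject held for bilirubin looks for the restart rule and finds only an enzyme limit, which that subject never exceeded.

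The stake is patient safety in a study whose primary objective is safety and tolerability. In Appendix 6 the follow-up cell can be taken to say that dosing may resume while the delay cell beside it says to wait. The same follow-up branch also returns the subject to routine monitoring, so following it would end the extra 48–72 hour testing. In Appendix 7 two sites with the same laboratory values could act differently, because the text gives neither of them a rule that fits.

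**Working it through.** The plan states no figure to reproduce. This is a check of rule logic, with all values in multiples of ULN.

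**Inputs (Appendices 6 and 7, hepatic tables)**

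| Item | Without liver metastasis | With liver metastasis |
|---|---|---|
| First row: discontinue | AST/ALT >3 and bilirubin >2 (or INR >1.5) | same |
| Hold, enzyme trigger | AST/ALT >12 to ≤20, bilirubin ≤2 | same |
| Hold, bilirubin trigger | >2 to ≤3 | >3 to ≤5 |
| Restart condition | AST/ALT ≤12 | AST/ALT ≤12 |
| Last row: discontinue | AST/ALT >20 or bilirubin >3 | AST/ALT >20 or bilirubin >5 |

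**Step 1: enzyme level in a bilirubin-only hold.** Both bilirubin bands lie wholly above 2. If AST/ALT were above 3, the first row would apply and treatment would stop. A bilirubin-only hold therefore has AST/ALT ≤3, and 3/12 = 25% of the restart limit.

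**Step 2: is the restart condition met when the hold begins?** The rows were applied to a grid of AST/ALT values from 1 to 21 and bilirubin values from 1 to 5.1.

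- Bilirubin-only holds without liver metastasis: AST/ALT in {1, 2, 3} and bilirubin in {2.1, 2.5, 3}, so 3 × 3 = 9 states. AST/ALT ≤12 at the start: 9 of 9.
- Bilirubin-only holds with liver metastasis: AST/ALT in {1, 2, 3} and bilirubin in {3.1, 4, 5}, so 9 states. AST/ALT ≤12 at the start: 9 of 9.
- Enzyme holds: AST/ALT in {13, 16, 20} and bilirubin in {1, 1.5, 2}, so 9 states in each table. AST/ALT ≤12 at the start: 0 of 9 in each.

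The condition works for the enzyme trigger and carries no information for the bilirubin trigger.

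**Step 3: Appendix 7 wording.** A return to ≤12 requires a starting value above 12. That is possible in 0 of 9 bilirubin-only states without liver metastasis and 0 of 9 with it. Read strictly, the branch cannot apply. Read loosely, as being at or below 12, it is met at once, as in Appendix 6. The other branches need an elevation that persists at the same level or worsens, so a bilirubin that has recovered meets none of them.

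**Step 4: Appendix 7 between days 8 and 28.** The restart branch closes at 7 days. The next branch, for >7 to ≤28 days, covers only values that stay at the same level. Recovery in that window has no branch for either trigger.

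**Step 5: is a bilirubin restart value given elsewhere?** Sections 7.4.1 and 7.4.2 point to the re-treatment criteria and the tables. Section 8.1.1 gives only the upper stopping limit. Appendix 8 covers CK and LDH; its hold at >15 to ≤20 does restart on the analytes that caused it ("If returns to \leq 15 xULN within \leq 28 days"). None gives a bilirubin value for restarting.

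**Step 6: does the proposed condition work?** Adding bilirubin ≤2 (≤3 with liver metastasis) makes the condition false at the start in all 9 + 9 bilirubin-only states, because each has bilirubin above that value. With liver metastasis, AST 4 and bilirubin 2.5 would pass the enzyme and bilirubin limits, yet that is a first-row discontinuation. A first-row check is therefore needed. It also covers INR, which the other limits do not.

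**The case against.** The strongest reply is that the row should be read as a whole. Its management cell says to delay while bilirubin is in the band. Bilirubin is retested every 48–72 hours, and Section 9.4.4 requires Day 1 results before dosing unless that is not locally feasible. A subject still in the band would simply be held again. The branch for elevations that persist beyond 28 days is not limited to enzymes, and immediate resumption would make it pointless for a bilirubin hold. Section 7.4.2 requires the event to have resolved, and here the event is the bilirubin. The Medical Monitor can be contacted at any time.

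Much of this stands. It rules out several stronger conclusions that a reader might draw:

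- **That Appendix 6 plainly authorises re-dosing anywhere in the bilirubin band.** It does not. The delay cell and the persistence branch point the other way, so this is an internal conflict.
- **That Appendix 7 forces a stop even after bilirubin normalises.** Its stopping branches need persistence or worsening. A normalised value falls in no branch at all.
- **That Appendix 7 leaves no route for any study drug.** Nivolumab alone may be considered in the >7 to ≤28 day step. It may also continue under the non-offending-drug footnote or where the cause is noninflammatory.
- **That every treated subject is exposed.** The tables govern everyone, but only a bilirubin-only hold meets the gap.
- **That every other laboratory hold restarts at the lower edge of its own band.** Grade 3 creatinine restarts at Grade 1 or baseline, which is stricter.

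The reply does not supply the missing value. The lower edge of the band can be inferred from the delay cell, but the follow-up cell states a different test, and Section 7.4.2 sends the reader back to that table. Contact with the Medical Monitor is optional under Section 7.4.2, and the Appendix 6 hold row mentions it only for elevations that persist or worsen.

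**Conclusion.** The point holds as a conflict and gap in the hold rows of all four hepatic tables. For a bilirubin-only hold, the Appendix 6 restart condition is already satisfied at the start with bilirubin unchanged. The Appendix 7 condition is either trivially satisfied or inapplicable, which leaves a recovered bilirubin without a rule for restarting cabiralizumab or the combination.

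The conclusion assumes that the first row takes precedence over the hold row, which is what caps AST/ALT at 3 x ULN. Even without that assumption, an isolated bilirubin rise would not normally be read as including AST/ALT above 12 x ULN.

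The size cannot be put as a number of subjects: the documents give no rate of isolated-bilirubin holds, and none is assumed. The practical risk is reduced by the safeguards above. A stated restart rule that tests the wrong analyte should still be corrected.

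**What to change.** Change the restart condition of the hold row as follows.

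- **Tables without liver metastasis (Appendices 6 and 7):** AST and ALT ≤12 x ULN, total bilirubin ≤2 x ULN, and the first row of the table not met.
- **Tables with liver metastasis (Appendices 6 and 7):** AST and ALT ≤12 x ULN, total bilirubin ≤3 x ULN, and the first row of the table not met.

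The bilirubin values are the levels at which the row's own trigger no longer applies; the sponsor should confirm them clinically. Keep the printed time limits (28 days in Appendix 6, 7 days in Appendix 7). In Appendix 7, also state what applies when values recover between day 8 and day 28.

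Section 6.1 admits subjects with Gilbert Syndrome with bilirubin below 3.0 x ULN, so a subject can enter already inside the >2 to ≤3 band. If a baseline exception is wanted for them, apply it to the hold trigger as well as the restart value. Otherwise the subject restarts and is held again at the next test.

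The cost is one condition in each of four tables and one added statement in each Appendix 7 table, with no new tests or visits. Some bilirubin holds will last longer. Appendix 12 records that Appendices 6 to 8 were aligned with another cabiralizumab protocol, which is not available here, so the sponsor should check whether it needs the same change.
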